# 9. Treatment effects monitoring

The ADAPT Treatment Effects Monitoring Committee is responsible for reviewing the accumulating data related to safety and efficacy. The committee will meet at least twice per year and they may elect to have *ad hoc* meetings or teleconferences at their own initiative.

The committee comprises both voting and non-voting members. The voting members are not involved in the conduct of ADAPT and are free of affiliations with the manufacturers of naproxen sodium or celecoxib bearing on the trial. The non-voting members are representatives of the study leadership and will include persons who are involved in implementation of the protocol as well as those involved in data analysis.

Monitoring reports of the accumulating data presented to the TEMC will include treatment group comparisons of baseline characteristics, incidence of AD, changes over time in cognitive measures, mortality, and adverse events. The TEMC will not be masked to treatment assignment in their deliberations regarding safety and efficacy. Stopping guidelines may be used in the decision-making process, but no formal curtailment rules based on p-values will be employed. However, stochastic curtailment approaches (based on conditional power and type I errors) may be used. The TEMC, with the advice and consent of the Steering Committee, will decide upon the approaches used for decision-making.

The TEMC may recommend stopping the trial before its planned conclusion if they observe convincing evidence of a treatment difference in adverse events or AD incidence. However, it is not expected that the TEMC will recommend stopping the trial early because of attenuation of decline in cognitive measures alone (i.e., without simultaneous demonstration of efficacy in reducing incidence of AD).

Recommendations of the TEMC will be forwarded by the Chair of the TEMC to the Chair of ADAPT. The recommendations will be communicated from there to the Study Officers and the Steering Committee. In addition, a summary report will be provided to the study IRBs. The Steering Committee will review the TEMC's recommendations. It is anticipated that the Steering Committee will approve the recommendations and then communicate them to the appropriate entities. In the event that the Steering Committee disagrees with the TEMC recommendations, the Steering Committee will follow the procedures outlined in the ADAPT policy statement on treatment effects monitoring.

# 10. Quality assurance and performance monitoring

#### 10.1. Overview

Quality assurance strategies for ADAPT include design strategies and monitoring activities. Design strategies include use of randomization to assign participants to treatment groups, masking data collectors to treatment assignment to the extent possible, requirement of certification of staff and sites, and formal training of staff in ADAPT procedures. Activities to monitor quality include performance monitoring, visits to field sites, and error detection procedures.

#### 10.2. Certification of field sites

Study investigators will be required to complete a field site certification form that provides detailed information with regard to the space, facilities, and personnel at the site. One purpose of the form is to serve as a checklist for staff of the resources that need to be in place when participant activities begin. One of the items requested will be a copy of the IRB notice of approval for ADAPT and copies of the stamped ADAPT consent statements to be used at the site. The information provided will be reviewed by Coordinating Center staff prior to certification of a field site for data collection.

#### 10.3. Training of staff

The Chairman's Office and Coordinating Center will train the physicians, nurses, coordinators, neuropsychologists and psychometricians in the standardized and uniform use of all assessment instruments prior to the randomization of participants in the trial. Training methods will include didactic instruction and clinical demonstrations. As appropriate, standardized methods for performing other study procedures will be outlined in the ADAPT Handbook and the ADAPT Neuropsychology Manual. Staff attending the training meetings will be responsible for training other staff at the field site in ADAPT activities.

#### 10.4. Certification of staff

The purpose of the staff certification program is twofold. It identifies to the Coordinating Center and to the study group the staff who will collect and/or record certain items of data for ADAPT and who will make decisions relating to eligibility for ADAPT. Second, it makes the data collector aware that he/she is a part of ADAPT and has a responsible and identifiable role in the trial.

Functions for which ADAPT will certify staff include director, associate director, coordinator, data system operator, neuropsychologist, participant contact coordinator, screening interviewer, study nurse, study physician and study psychometrician. The listing of certified functions results from recognition that some data for the trial will be collected by ADAPT staff at the field sites, while other data may be collected under the ADAPT protocol but by staff not directly employed by ADAPT.

# 10. Quality assurance and performance monitoring

All certified staff will be required to read the consent forms, protocol and handbook, to complete a form identifying the functions for which they are applying for certification in ADAPT, and to complete a Knowledge Assessment form. They will be asked to sign a statement acknowledging that they have read the study materials; that they understand that ADAPT is a collaborative activity and that results will not be available until the trial is terminated; that they will adhere to high standards of integrity in the data collection, recording, and editing processes; and that they will treat all ADAPT data as privileged information and thereby protect the confidentiality of the study participants and the collaborative research team. Certification for neuropsychological testing and data entry will require achievement of a set standard of performance. Each staff member certified for one or more functions for ADAPT will be issued a personal identification number; this number will be recorded as required when completing data collection forms.

#### 10.5. Performance monitoring

Performance monitoring will begin with the initiation of participant screening and will continue throughout the duration of the trial. Field sites will be monitored on a regular basis regarding the following:

- Rate of enrollment
- Protocol deviations
- Missed visits
- Losses to followup
- Completeness of data
- Percentage of data items requiring edit queries
- Percentage of discrepancies found in audited data items

Summaries of the above measures will be provided to the field sites and to NIA on a regular basis and to the TEMC whenever they meet. Review of performance data will be an agenda item for all Steering Committee meetings.

#### 10.6. Site visiting

Site visits will be made to each of the field sites early in the course of recruitment and at regular intervals (probably yearly). The site visitors will review consent forms for enrolled participants, study documents, IRB approvals, scheduling and logistics, staffing, adverse events, protocol issues, forms management, data management, specimen shipment, and study drug accounting.

# 10. Quality assurance and performance monitoring

#### 10.7. Error detection

The study will employ double data entry to reduce the occurrence of errors. In addition, extensive range and logic checks will be done during data entry, and these checks may be continually updated throughout the trial to address new data problems as they are discovered. Edit queries will be made to the field sites on a regular basis regarding inconsistencies that were not resolved at data entry. Periodically, additional batch edits related to consistency of data across forms and over time will be generated.

Periodic audits of subsets of the ADAPT database will be conducted, both through visits to the field sites and through a remote auditing procedure. At on-site visits, participant data will be chosen for verification from source documentation. For the remote auditing procedure, field sites periodically will be asked to send copies of the ADAPT participant form sets to the Coordinating Center, and the data on the forms will be checked against the database for discrepancies. The electronic log of attempted randomizations will be reviewed periodically at the Coordinating Center and field sites will be questioned about unusual occurrences.

# **ADAPT Protocol**

# 11. Investigational new drug application

The trial is being conducted under Investigational New Drug (IND) number 60,739 which is held by the ADAPT Chair. Protocol amendments will be submitted to both the FDA and NIA. The study leadership is also responsible for meeting reporting regulations of the FDA with regard to adverse events and annual reports.

# 12. Protection of human subjects

## 12.1. Monitoring of IRB approval process

The IRB serving the Johns Hopkins University Bloomberg School of Public Health is considered the parent IRB for ADAPT. Prototype consent materials for ADAPT will be provided by the Coordinating Center. Field sites may add information and reformat information to conform with their local requirements, but deletion of information will not generally be permitted.

One of the requirements for certification of a field site to begin participant activities will be submission of the site's notice of IRB approval and a copy of each stamped consent form used at the site. These materials will be reviewed by Coordinating Center/Chairman's office staff for conformance with the prototype materials and deviations will be questioned as appropriate.

Field sites that have obtained IRB approval for a previous version of the protocol will inform their IRB of changes to the protocol. Protocol amendments and changes to the consent form will be distributed from the Coordinating Center via numbered memos. These amendments and changes will be submitted by the field sites to their IRB in writing. All adverse events thought to be related to study treatment and all serious adverse events, regardless of presumed relationship to the experimental treatment, will be reported to the parent IRB as well as to the field site IRBs.

#### 12.2. Consent process

The consent process for ADAPT is perceived as a dialogue between participant and ADAPT staff, supported by discussions and written materials.

Prototype written materials include four separate consent forms for the participant and one consent form for the collateral respondent. The consent forms are designed to be introduced at specific points in the screening, enrollment, and followup process.

The consent for eligibility evaluation is signed at the first visit (eligibility evaluation visit). The participant is asked to sign this statement at the same visit at which he/she first sees the statement. Also at this visit, the collateral respondent is asked to sign a consent form.

In addition, the consent form for enrollment and the consent for genetic testing and DNA banking are reviewed with the participant at the eligibility evaluation visit. The participant is given unsigned copies of the consent forms to take home. The forms are then reviewed again with the participant and signed at the enrollment visit.

If at any visit a participant needs a referral for a dementia evaluation, the consent form for the cognitive testing and diagnostic evaluation will be discussed with the participant and his/her collateral respondent. The consent form will be signed at the time of the dementia evaluation visit.

#### 12. Protection of human subjects

#### 12.3. Risks and potential benefits to participants

**Risks**: There are risks to participation in ADAPT for each treatment group. Like all participants, those assigned to placebo will be asked to limit the use of NSAIDs and other medications (see section 3.3). Thus, participants in this group may have an increased burden of pain or inflammation, for example.

Participants assigned to receive naproxen sodium or celecoxib may experience adverse effects of the study drug, such as water retention, increased blood pressure, stomach irritation, gastrointestinal bleeding, anemia, renal toxicity, or hepatotoxicity. The risk of serious adverse events is expected to be higher in the naproxen sodium group than in the celecoxib group.

The above risks are outlined in the Participant Consent Statement for Enrollment (see Appendix C). Participants are told that they may withdraw from the study at any time and that they may stop the study drug in order to take proscribed medications. Safety monitoring is described in section 12.4.

**Potential benefits**: If one or both of the active study treatments are found to be efficacious, participants taking the efficacious treatment(s) may benefit from delayed onset or prevention of AD. It also is possible that participants receiving naproxen could benefit from a lower risk of heart attack, stroke, and certain cancers, although these effects are still under investigation.

All participants may benefit from the regular, ongoing, medical monitoring and referrals (when indicated) that they will receive in ADAPT. Those who develop dementia while in the trial may benefit from early diagnosis, which could facilitate appropriate treatment and care. In addition, all participants may benefit from the satisfaction of contributing to medical knowledge.

Alternatives to participation: Because ADAPT is a primary prevention trial, there is no direct alternative to participation. Other primary prevention trials are in progress, but the geographical location of the participating sites for the most part does not coincide with that of the ADAPT sites. Because the study medications are available either over the counter (naproxen sodium) or by prescription (celecoxib), people interested in the prevention of AD could self-medicate. However, given the unknown safety and efficacy of such use, it is not an advisable alternative to study participation.

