Appendix B: Design summary (same changes as outlined above)

### Participant Consent Statement for Enrollment:

"Some doctors have suggested that people taking celecoxib have an increased risk of a heart attack or stroke. There is a debate among doctors about whether this risk is real. The doctors who run ADAPT do not think the evidence for this risk is convincing. Since you may be assigned to take celecoxib, you should know of the current debate about its risks. If we learn more about these risks (or if we learn that they are not real risks) we will tell you about the new information on this topic." was added

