### **Secondary objectives**

- To determine whether the study treatments can attenuate cognitive decline with aging
- To compare the safety of the study treatments with placebo, and with each other, regarding mortality and the occurrence of side effects

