#### 8.3. Analysis of other outcomes

Other outcomes to be investigated include measures of cognitive function, mortality, and the occurrence of adverse events. Comparisons of cognitive function between treatment groups will employ longitudinal data analysis techniques (generalized estimating equation (GEE) regression) described by Liang and Zeger that account for the within-subject correlation. This method generates robust estimates for the variance without relying on specific assumptions about the correlation structure. It also allows for the use of a treatment effect indicator along with adjustment for multiple confounders and treatment effect modifiers in the comparison of the patterns of cognitive decline in

8. Analysis plan

the two treatment groups. The outcome measure in the regression model will be the rate of change from baseline in the cognitive screening scores, calculated at each time that the tests are administered. To protect against influence of outliers, the ranks of the rates of decline will be used for the determination of p-values.

Survival analysis methods will be used to compare mortality in each of the treatment groups to that in the placebo treated group. If mortality is differential by treatment group, further analysis will be done to determine the effect of the differential mortality on the primary analysis of AD incidence.

The frequency and nature of adverse events will be described in two ways. Descriptive analyses will summarize the occurrence in each of the treatment groups of adverse events noting their frequency, severity, and major organ system involvement. Another analysis will focus on prediction and explanation of adverse events using a composite outcome variable. That is, participants' cumulative history of adverse events during the trial will be classified as mild, moderate or severe. The frequency of these outcomes will be formally compared between the treatment groups. Chisquare statistics and related methods for ordinal categorical variables will be used. In addition, logistic regression models will be used to adjust the frequency of adverse events between the treatment groups for imbalances and baseline predictor variables (if any).

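### The enrollment consent discloses a debated heart attack and stroke risk with celecoxib, but section 12.3 does not list it and no cardiovascular outcome is named for comparison

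*Protocol*

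**What the plan says.** **Risk text.** Section 12.3 gives the possible adverse effects of either active drug as effects "such as water retention, increased blood pressure, stomach irritation, gastrointestinal bleeding, anemia, renal toxicity, or hepatotoxicity". Heart attack and stroke appear in that section once, under potential benefits, where "participants receiving naproxen could benefit from a lower risk of heart attack, stroke, and certain cancers".

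**Consent.** The Document history for version 1.3 records an addition to the enrollment consent: "Some doctors have suggested that people taking celecoxib have an increased risk of a heart attack or stroke". It describes this as a debate, adds "The doctors who run ADAPT do not think the evidence for this risk is convincing", and says participants will be told if more is learned. The consent changes listed for version 1.4 do not withdraw it.

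**Objectives and analysis.** The safety objective in section 2 compares the treatments with placebo and with each other "regarding mortality and the occurrence of side effects". Section 8.3 opens with "Other outcomes to be investigated include measures of cognitive function, mortality, and the occurrence of adverse events". Mortality is compared by survival methods. Adverse events are handled in two ways. One is a descriptive summary by group, "noting their frequency, severity, and major organ system involvement". The other is a formal comparison of each participant's cumulative adverse event history, graded mild, moderate or severe.

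**Monitoring.** Section 9 lists the group comparisons reported to the Treatment Effects Monitoring Committee (TEMC): baseline characteristics, "incidence of AD, changes over time in cognitive measures, mortality, and adverse events". The outcome list in Appendix B likewise has no cardiovascular item.

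**The concern.** The protocol treats heart attack and stroke in three ways that do not fit together. The consent raises them as a debated celecoxib risk, section 12.3 raises them only as a possible naproxen benefit, and the analysis and monitoring sections do not name them.

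The trial gives celecoxib, naproxen or placebo for up to 7 years to people aged 70 or older, so it is well placed to inform the question that the consent leaves open. If no comparison is named in advance, the evidence on that question comes from a general adverse event summary and from an all-cause severity grade in which cardiovascular events are mixed with every other severe event. A real difference could then be slower to emerge. Any cardiovascular comparison made later would have to be defined after the data had been seen.

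**Working it through.** The plan states no cardiovascular figure, so there is none to reproduce. The check is a comparison of the texts followed by two illustrations of scale.

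**1. Texts side by side**

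| Place | Heart attack and stroke |
|---|---|
| Enrollment consent (version 1.3 addition) | Debated celecoxib risk; participants to be told of new information |
| Section 12.3, risks | Not listed |
| Section 12.3, potential benefits | Possibly lower with naproxen |
| Section 2, safety objective | Not named |
| Section 8.3, other outcomes | Not named |
| Section 9, TEMC reports | Not named |
| Appendix B, outcomes | Not named |

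Section 12.3 states that the risks it gives are set out in the enrollment consent. The reverse does not hold, because the consent contains a risk that 12.3 lacks. The version 1.3 log also shows that the benefit sentence in 12.3 was narrowed from active treatment in general to naproxen. The same revision therefore dealt with this topic in both places, but the risk list did not follow.

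**2. What a named comparison could show (illustration)**

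Inputs from the protocol: 2,625 participants at 1:1:1.5, which is 750 per active group and 1,125 on placebo; mortality of 4% in year 1, rising by a factor of 1.085 a year; 5% loss a year. Assumed, because the protocol gives no figures: event rate λ and hazard ratio (HR). Non-adherence is ignored. All deaths count as exits, so cardiovascular death is not an event here.

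For years y = 0 to 6, the exit hazard is k = −ln(1 − 0.04 × 1.085^y) − ln(0.95) + λ. Expected events are n × Σ S × λ × (1 − e^−k)/k, where S starts at 1 and is multiplied by e^−k each year. Power is Φ(|ln HR| × √(0.4 × 0.6 × events) − 1.96).

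- One event, 1% a year on placebo, HR 1.5: 54 + 55 = 109 events; 0.405 × √(0.24 × 109) − 1.96 = 0.11; power about 55%.
- Both events combined, 2% a year, HR 1.5 for each: 104 + 107 = 211 events; 0.405 × √(0.24 × 211) − 1.96 = 0.92; power about 82%.
- Both combined, only one event raised: 2.5% against 2% a year, HR 1.25; 88 + 107 = 195 events; 0.223 × √(0.24 × 195) − 1.96 = −0.43; power about 33%.

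| Placebo rate, each event | One event, HR 1.5 | Combined, both raised | Combined, only one raised |
|---|---|---|---|
| 0.5% a year | 32% | 55% | 19% |
| 1.0% a year | 55% | 82% | 33% |
| 1.5% a year | 71% | 93% | 45% |

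After 3 years at 1% a year each, the figures are 33% for one event and 56% for the two combined if both are raised.

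**3. What the fixed severity classification would show (illustration)**

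Assume a cumulative placebo risk c of heart attack or stroke, raised 1.5-fold on the active drug, with every such event graded severe. Let s be the placebo share with any severe event. Other severe events then have probability o = (s − c)/(1 − c) in both groups, and the active share is 1 − (1 − o)(1 − 1.5c).

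For c = 5% and s = 20%: o = 0.158, and the active share is 1 − 0.842 × 0.925 = 22.1%. Comparing 20% of 1,125 with 22.1% of 750 (two-sided 0.05, pooled variance under the null) gives about 20% power. Comparing 5% with 7.5% directly gives about 60%.

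| Placebo risk c | Cardiovascular comparison | Severe share, s = 20% | s = 30% | s = 40% |
|---|---|---|---|---|
| 5% | 60% | 20% | 13% | 10% |
| 10% | 90% | 63% | 43% | 30% |

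This reduces the ordinal classification to severe against not severe, so it shows the direction and rough size of the dilution only.

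**The case against.** The strongest case against has five parts.

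- **The 12.3 list is illustrative.** It is introduced as examples and already includes raised blood pressure and water retention. Participants get their risk information from the consent, which does mention heart attack and stroke. This stands. A reader might infer that participants are not told of the risk, and the documents do not support that.
- **The consent reports a debate.** It says that the investigators are not convinced, and 12.3 calls the naproxen benefit still under investigation. This stands too. It would go too far to say that the protocol expects opposite cardiovascular effects in the two active groups.
- **The TEMC already sees the data.** It is unmasked, meets at least twice a year, receives adverse events and mortality by group, and may recommend stopping for a difference in adverse events. So the promise of new information does have analysis behind it. Nor does 8.3 say that heart attack and stroke would fall in separate rows of a table. It mentions organ system but fixes no layout.
- **Naming a safety outcome belongs in the analysis plan.** This stands in part. A separate plan could add one. But 8.3 does not leave the method open: it chooses the formal adverse event comparison, and that choice is poorly suited to this question.
- **The power figures rest on assumptions.** Rates and hazard ratios are assumed, non-adherence would lower the power, and the combined outcome loses if only one component is raised. P-values are also descriptive under 8.1, so power does not measure what the TEMC would recognise. All of this stands, which is why the figures are illustrations and the components must be shown separately.

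**Conclusion.** The point holds as a mismatch between sections and an avoidable weakness in the safety analysis, not as a failure of disclosure or of data collection. The consent raises a debated risk, section 12.3 does not carry it, and no section names an outcome that would address it. Cardiovascular events would reach the TEMC as adverse events and deaths, but the one formal adverse event comparison that is fixed would dilute a difference in them.

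The size depends on assumed event rates. With a 5% cumulative placebo risk and a 1.5-fold increase, power is about 60% for a direct comparison and 10% to 20% for the severe share. The gain from combining heart attack and stroke, about 55% to 82% at 1% a year each, requires both to be raised. The consent wording is known here only from the Document history, as text added and not later withdrawn. This is a worthwhile, inexpensive improvement.

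**What to change.** 1. Reconcile the section 12.3 risk list with the enrollment consent, so that both refer to heart attack and stroke with celecoxib and both say that the risk is debated.
2. In section 8.3, name time to first heart attack, stroke or cardiovascular death as a safety outcome, with a definition of each component. Analyse it by assigned treatment with survival methods, for each drug against placebo and for the two drugs against each other, as the safety objective already provides. Show heart attack and stroke separately as well.
3. In section 9, include this outcome and its components in each TEMC report, and add it to the outcome list in Appendix B.

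The cost is a short protocol amendment and one added table and survival analysis per report. The events already fall within adverse event and mortality reporting, so no new visits and no change in sample size are needed.
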